CASTomize Pilot Study Protocol

Principle investigator: [name]

Co-investigator: [name], [name]

Industrial collaborator: [name], [name], [name]

CASTomize pilot study protocol: a randomized controlled trial comparing CASTomize 4D printed cast versus standard of care fiberglass cast on fracture reduction and patient reported outcomes.

Abstract

Background: For many years, traditional fibreglass casting has been the gold standard of immobilisation for distal radius fractures (DRFs). However, the traditional method of casting has obvious disadvantages such as poor patient comfort, inability to be in contact with water, difficulty observing skin underneath and requiring multiple cast changes in the patients care journey. This study compares the Castomize 4D printed casts versus the conventional fiberglass cast in fracture immobilisation, and various patient reported outcomes.

Methods/design: This study is a randomised control trial comparing Castomize 4D printed cast versus conventional fibreglass casts in isolated conservatively treated distal radius fractures. The primary outcome measure is fracture reduction. Secondary outcome measures include patient reported outcome measures such as the Adult Rated Cast Evaluation Questionnaire (ARCEQ)[1][2], comfort of the cast, quality of life assessed with the EQ-5D-5L questionnaire[3], cost-effectiveness and adverse events occurrence. In total, 30 patients will be included and followed for 6 months.

Trial registration: Pending

Registration number: Pending

Background

Displaced distal radius fractures (DRF) are very common in the adult population and their incidence is still on rising trend due to aging population. This is an issue which is pervasive across all ages, but most common in the elderly. In 2019, 180 million fractures happened worldwide. An average of 5 fracture incidents occurs every second. The current gold standard in fracture immobilisation is via the application of a fibreglass cast. However, the current fibreglass cast has multiple disadvantages. The cast is bulky, has poor ventilation and cannot come into contact with water. This gives patients considerable discomfort, and are unable to bathe and provide hygiene to their injured limb for the duration of the casting. Because the cast is not breathable, skin maceration, itchiness and wounds

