may become an issue. In this light, multiple casts changes become necessary to reduce the risk of soft tissue complications and to provide patient comfort. This increases the wastage of materials for the fibreglass casting as well as increases healthcare burden for the cast changes.

Castomize has created a 4D printed cast with its proprietary materials and designs aimed at overcoming the challenges in the traditional casting methods. Its 4D printed casts are lightweight and breathable, allowing contact with water and hygiene. Its design facilitates visualisation of the skin and soft tissue conditions. It is also remouldable, potentially only requiring one device for the duration of the patients care journey.

The design of the 4D printed cast was done in collaboration with orthopaedic clinicians, prosthetists and senior casting technicians optimised for clinical use. A biomechanical test was performed to evaluate the biomechanical properties of the 4D printed cast in comparison to the conventional fibreglass casts and were found to be less stiff and with a lower load to failure. This was however accessed to be not clinically significant.

Therefore, this study aims to compares the Castomize 4D printed casts versus the conventional fiberglass cast in fracture immobilisation and various patient reported outcomes.

Methods/design

This manuscript is written according to the Consolidated Standards for Reporting Trials (CONSORT statement) and Standard Protocol Items: Recommendations for Interventional Trials (SPIRIT guidelines).

Objectives

The primary aim of the study is to assess non inferiority of the Castomize 4D printed cast versus conventional fibreglass casts in fracture immobilisation and reduction.

The secondary aim of the study is to assess differences in patient reported outcomes measures (ARCEQ, comfort of the cast, EQ-5D-5L, cost-effectiveness and adverse events occurrence) in the Castomize 4D printed cast versus conventional fibreglass casts.

Design, participants, interventions and outcomes

Study design and randomization

A randomised controlled trial will be conducted in a single institution: TTSRH.

Patients will be recruited at the outpatient clinic. Patients who meet the inclusion and exclusion criteria will be recruited and randomised into 2 groups. Randomisation will be carried out via block randomisation via a computer generated randomization sequence.

Group 1: Castomize 4D printed cast (Figure 2)

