Patients randomized to group 1 will undergo fracture immobilisation with the Castomize 4D printed cast via the care team (Casting technician/ clinical team). The Castomize 4D printed cast is appropriately heated and then moulded to the patients wrist as per usual manipulation and reduction techniques. The cast is held in position until hardened.

Group 2: Conventional casting (Figure 1)

Patients randomized to group 2 undergo fibreglass casting as per the standard of care.

In both groups, post casting X-rays are taken to assure fracture reduction and recasting may be attempted in the event of inadequate fracture reduction.

A patient information sheet will be provided to the patient explaining the study protocol, and what to look out for in caring for their casts.

Inclusion criteria

- Age \geq 21 years
- Distal radius fracture for conservative treatment within 3 weeks of initial injury

Exclusion criteria

- Concomitant injuries to the ipsilateral extremity, interfering with the treatment of the DRF (Example: concomitant elbow fracture that requires further immobilisation with a above elbow cast)
- Inability to complete study forms due to any cognitive, mental issues.
- Pregnant women

Study procedures and timeline

Measurements will take place at 6 time points as shown in Table 1. These time points are baseline (T0), 1 week (T1), 2 weeks (T2), 6 weeks (T3), 3 months (T4) and 6 months (T5) after inclusion in the study. At T0, baseline characteristics will be gathered. An inclusion form will be filled in by the treating physician providing fracture and treatment-specific information. Second, patients receive a questionnaire, providing predominantly patient and injury-specific information. The list of baseline characteristics is shown in Table 2. Patients receive questionnaires at T1 to T5. These questionnaires are carried out by phone call. Posterior-anterior (PA) and lateral radiographs of the wrist will be taken at T0 (before and after reduction) and during follow-up at T1 –T4 as per standard of care. Physical examination of the wrist will take place at T4 and will be performed by the research team. Study visit may be administered via phone call. Functional tests will be performed at patient earliest appointment.

Table 1 Schedule of activities

	T0 Baseline	T1 D7 \pm 3	T2 D14 \pm 3	T3 D35 \pm 7	T4 D84 \pm 14	T5 D168 \pm 21
Inclusion form	✓					
X-rays*	✓	✓	✓	✓	✓	
Functional tests**					✓	✓
VAS		✓	✓	✓	✓	✓
Photograph		✓				
Comfort of cast		✓	✓	✓		

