Analgesic use		✓	✓	✓	✓	✓
EQ 5D5L		✓***		✓	✓	✓
ARCEQ				✓	✓	✓
MCQ- iMTA				✓	✓	✓

PCQ- iMTA				✓	✓	✓
-----------	--	--	--	---	---	---

*X-rays before and after reduction (obtained from standard of care results if available)

**ROM, grip strength done by study team. ROM, DRUJ and Kapandji will be collected as part of standard of care if available

*** EQ 5D5L status pre-fracture and post-fracture sustainment

Table 2 Baseline characteristics

Baseline characteristics	
Date of emergency room visit	Sex
Affected wrist	Date of Birth
Method of reduction	
	Hand dominance
	Mechanisms of injury
	Smoking Status
	General medical history
	Previous injuries of the affected extremity
	La Fontaine criteria

Outcome

Primary outcome The primary outcome of this study is the occurrence of fracture displacement assessed on PA and lateral radiographs at 1, 2 and 6 weeks. Displacement of the radius is defined by: As compared to the post reduction radiograph at T0, Displacement of : > 15° of dorsal angulation, > 20° of volar angulation, < 15° of radial inclination, > 3mm of radial shortening and > 2mm intraarticular step-off or gap. Measurements will be on standard PA and lateral radiographs of the wrist by trained members of the research team.

Secondary outcomes An overview of measurements is shown in Table 1.

- Comfort of the cast assessed via pictorial representation of pressure marks or areas of discomfort.
- Severity of pain evaluated with the Visual analogue Score (VAS)
- Patient will describe their average wrist symptoms over the past week on a scale of 0-10 using Adult Rated Cast Evaluation Questionnaire (ARCEQ) [6][7].
- Quality of life will be assessed using the 5-level EuroQol (EQ-5D-5L) scoring questionnaire.
- Cost-effectiveness will be measured using the Medical Consumption Questionnaire (iMCQ) and the Production Consumption Questionnaire (iPCQ) [8].
- Physical examination:
 - Range of motion (ROM) of the wrist will be measured with a goniometer. ROM concerns dorsal flexion, volar flexion, radial deviation, ulnar deviation, pronation and supination.
 - Grip strength will be measured with a Jamar hydraulic hand dynamometer. The maximum score for each side over 3 attempts will be used
 - Specific testing of the wrist and hand will be performed namely:
 - distal radioulnar joint (DRUJ) stability tested with the DRUJ ballottement test

- opposition of the thumb using the Kapandji score

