- finger stiffness will be measured with finger-to-palm distance, tested from the tip of the finger to the distal palmar crease when the fingers are in maximal active flexion

ROM and grip strength on the injured side will be compared with the uninjured side.

- Number of conversions to surgical treatment and other (serious) adverse events will be monitored. (Eg: Skin complications)

It is expected that a proportion of patients will fail conservative treatment with displacement of the distal radius fracture at week 1 or week 2 follow up. These patients will continue with surgical fixation of their fractures and no further trial procedures will be required.

Adverse events reporting

All adverse events reported by the patient or observed by the treating physician or researcher will be recorded. Serious adverse events (SAE) will be reported to the Domain Specific Review Board (DSRB), which approved the protocol.

Serious adverse events are defined as:

- Skin related problems requiring surgical intervention (Eg: Ulcer, infection, necrosis)
- Compartment syndrome
 - Cast related injury to the patient resulting in loss of limb or life

Study related serious adverse events are defined as:

- Compartment syndrome

Fig 1 Conventional Fiberglass cast[9]

Fig 2 CASTomize 4D printed cast

Data analysis

General descriptive statistics will be performed on baseline patient and fracture characteristics. Patients will be analysed according to the intention-to-treat principle.

Primary outcome

The primary outcome, fracture re-displacement, will be analysed using a mixed-effects logistic regression. To account for clustering, a random intercept for the hospitals will be used. Fixed effects will be the covariates we adjust for as reported in the literature, namely age, presence of osteoporosis, and fracture characteristics. If new prognostic factors will be identified and reported in the literature, these factors will also be added as covariates.

Secondary outcomes

For secondary outcomes, trends between baseline and follow-up time points (T0-T5) will be assessed using linear mixed models for repeated measures. This accounts for comfort of the cast, recovery of function and grip strength, pain severity (VAS), ARCEQ and EQ-5D-5L scores. The number of conversions to surgical fixation and complications will be determined using Fisher Exact or Chi-square test, depending on the magnitude of results.

Cost-effectiveness analysis

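### Minor skin events and visible pressure marks are not looked for equally in the two arms, so the comparison of skin complications can partly reflect opportunity to detect

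*Combined protocol and SAP*

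**What the plan says.** On visibility and cast changes, the Abstract's Background paragraph lists among the drawbacks of conventional casting "difficulty observing skin underneath and requiring multiple cast changes in the patients care journey". Of the 4D cast, the Background section says "Its design facilitates visualisation of the skin and soft tissue conditions" and describes it as "potentially only requiring one device for the duration of the patients care journey".

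On the outcomes, the Objectives include comfort and adverse events among the secondary between-arm comparisons. Under Outcome, Secondary outcomes, the comfort item reads "Comfort of the cast assessed via pictorial representation of pressure marks or areas of discomfort", and skin complications are the named example of a monitored adverse event.

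On ascertainment, Adverse events reporting states: "All adverse events reported by the patient or observed by the treating physician or researcher will be recorded". In Table 1 the row "Comfort of cast" is ticked at T1, T2 and T3, and a photograph is ticked at T1 only. Of the questionnaires at T1 to T5, Study procedures and timeline says "These questionnaires are carried out by phone call", and it allows study visits by phone as well. Table 1 names no cast-removal visit and no skin inspection with the cast off.

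On analysis, the Data analysis section compares complications by Fisher's exact or Chi-square test, with no allowance for unequal detection.

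**The concern.** The device feature under test, visible skin, changes how readily one of the outcomes is noticed. A mild pressure mark, patch of maceration or abrasion that causes no symptoms enters the data only if someone sees it. In the 4D arm it may be seen through the cast. In the fibreglass arm it will mostly be seen when the cast is changed or removed. The number of such occasions is also expected to differ by arm, and none is scheduled by the protocol.

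A difference in minor skin events could then arise with no difference in harm, and similar counts could hide a real difference. With 30 patients, two or three events would shape how skin safety is read. The loss cannot be repaired at analysis, because skin that was never inspected leaves no record.

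**Working it through.** **Reading the passages together**

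| Feature | 4D arm | Fibreglass arm |
|---|---|---|
| Skin visible with cast on | Made easier by the design | Difficult, not said to be impossible |
| Cast changes exposing the skin | Potentially none (one device) | Multiple, unscheduled |
| Out-of-cast skin check at a common point | None scheduled | None scheduled |
| Capture of minor events | As reported or observed | As reported or observed |

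The opportunities to detect differ in kind (continuous view through the cast against intermittent full exposure) and in number. Nothing in the plan equalises them.

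**Illustration of size**

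The documents give no skin-event rate and no detection probability, so there is no figure of the plan's own to reproduce. From the documents: 30 patients in two groups. Assumed: 1:1 allocation (15 per arm, since the ratio is not stated), a two-sided 5% Fisher test, and the rates below.

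Observed rate = true rate × probability of detection. With the same true rate p in both arms, full detection in one arm and detection d in the other, the spurious risk difference is p × (1 − d).

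At p = 30% the fully observed arm expects 15 × 0.30 = 4.5 events. Exact binomial enumeration gives:

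| d in the less well observed arm | Expected events, better vs less well observed | Spurious difference | Better observed arm shows more events | Fisher rejects |
|---|---|---|---|---|
| 1.00 | 4.5 vs 4.5 | 0 points | 42% of trials | 1.7% |
| 0.75 | 4.5 vs 3.4 | 7.5 points | 60% | 2.9% |
| 0.50 | 4.5 vs 2.25 | 15 points | 78% | 7.8% |
| 0.25 | 4.5 vs 1.1 | 22.5 points | 92% | 20% |

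At d = 0.50, true rates from 10% to 50% give spurious differences from 0.10 × 0.5 = 5 points to 0.50 × 0.5 = 25 points.

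The arms are labelled by detection, not by device, because the documents do not settle which is better observed. The table applies either way round.

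**Masking**

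If the true rates were 20% (4D) and 40% (fibreglass) and half the fibreglass events were missed, the expected counts would be 15 × 0.20 = 3.0 and 15 × 0.40 × 0.5 = 3.0, and a real benefit would disappear. With rates and detection reversed between the arms, the same arithmetic would hide a real harm.

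**The case against.** The strongest reply is that the imbalance is narrower than it looks and its direction unknown. Much of that stands, and it limits what may be inferred.

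- A reader might infer that skin cannot be seen under fibreglass, so minor events are over-counted in the 4D arm. The protocol says only that observation is difficult, and it expects repeated fibreglass changes, each of which exposes the skin. The 4D arm may have fewer full exposures. Earlier sight of a mark might also prevent it from progressing, which would be a real device effect. No direction can be asserted.
- A reader might infer that the comfort comparison is a measure of visibility. Its definition also admits felt discomfort, it is listed with the patient-reported outcomes, and a patient can indicate where a cast hurts without seeing the skin. Only the pressure-mark part is exposed to the problem. That the picture has no stated scoring rule is a separate matter.
- A reader might infer that the single T1 photograph drives the skin comparison. The plan does not say what is photographed, whether the cast is on or off, or which outcome it serves.
- A reader might infer that adverse events count only while the cast is worn. No such limit is stated: lesions found at a change or at removal count in both arms, and symptomatic ones can be reported in either.

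It is also fair that the detection probabilities above are invented and that Fisher's test with 15 per arm seldom rejects at these rates. The main risk is therefore misreading small counts, not false significance.

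None of this equalises ascertainment. Unscheduled cast changes that differ in number by arm are a further source of inequality, and an unknown direction makes the comparison harder to interpret.

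**Conclusion.** The point holds for minor observed skin events and visible pressure marks. On the protocol's own description, the arms differ in how easily and how often skin is seen, and no common out-of-cast check corrects for it. The planned test of skin complications can therefore partly reflect opportunity to detect.

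The size cannot be estimated from the documents. Under the stated assumptions, missing half the events in one arm creates a spurious difference of 5 to 25 points for true rates of 10% to 50%, in a direction that is not established.

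Felt discomfort, the skin events classed as serious because they need surgery, and compartment syndrome depend little on visibility. The radiographic primary outcome is little affected. This is a weakness in one part of the secondary outcomes of a pilot, and worth correcting before enrolment because the missing observations cannot be recovered later.

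**What to change.** - **Table 1:** name the final cast-removal visit and add one out-of-cast skin check with a photograph in both arms, on the same checklist, either by moving the T1 photograph there or by repeating it. Make this the between-arm comparison of skin findings.
- **Patients converted to surgery:** the Outcome section ends trial procedures for them, so state that the same check is recorded when the cast is removed before fixation.
- **Adverse events reporting:** keep recording all in-cast skin findings for safety. Label each by how it was detected (seen through the cast, at a cast change, at removal, or patient-reported) and report them descriptively by arm.

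The cost is small: an added Table 1 entry, a short checklist, one photograph and a few sentences of text. The cast has to come off in either arm, but because removal is not in the schedule and visits may be by phone, the visit must be named and attended in person. The downside is that transient marks that resolve before removal drop out of the formal comparison and appear only in the descriptive safety listing.

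### The grip model should include whether the dominant hand was injured: a minor precision gain from data already collected, not a correction of bias

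*Combined protocol and SAP*

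**What the plan says.** - Outcome, Secondary outcomes (physical examination): "ROM and grip strength on the injured side will be compared with the uninjured side". For grip, "The maximum score for each side over 3 attempts will be used". Whether the comparison is a ratio or a difference is not stated.
- Table 2 lists "Affected wrist" and "Hand dominance" among the baseline characteristics.
- Data analysis, Secondary outcomes: "trends between baseline and follow-up time points (T0-T5) will be assessed using linear mixed models for repeated measures", and "This accounts for comfort of the cast, recovery of function and grip strength, pain severity (VAS), ARCEQ and EQ-5D-5L scores". No covariates are named. The only covariate list (age, osteoporosis, fracture characteristics) belongs to the primary outcome and omits dominance.
- Table 1 ticks functional tests at T4 and T5 only, so there is no baseline grip. The text under Study procedures and timeline places the physical examination at T4.
- Study design and randomization: "Randomisation will be carried out via block randomisation via a computer generated randomization sequence". No stratification factor is given.
- Abstract: "In total, 30 patients will be included and followed for 6 months".

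**The concern.** With no grip value at T0, the uninjured hand is the only reference for recovery. If the dominant hand is normally stronger, the injured/uninjured comparison looks better when the dominant wrist was broken and worse when the other one was. That spread between patients has nothing to do with the cast. The plan collects the two items needed to remove it but gives them no stated use beyond describing the sample. In a trial this small, the share of dominant-side fractures can differ noticeably between arms, and the observed grip difference would then partly reflect which hand was broken.

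**Working it through.** The plan gives no figure for grip, function or dominance, and no calculation behind its 30 patients, so there is nothing of its own to reproduce. The check below is on the ratio scale, as an illustration.

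**Inputs**
- From the documents: 30 patients, two groups.
- Assumed: 1:1 allocation (15 per arm); half of the fractures on the dominant side (p = 0.5); dominant hand stronger by k = 0–15%; mean injured/uninjured ratio apart from dominance R = 0.70–0.85; residual SD 20 points (15 points as an alternative).

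**Step 1: gap between dominant- and non-dominant-side fractures.** The expected ratio is R(1+k) if the dominant hand is injured and R/(1+k) if not, so gap = R[(1+k) − 1/(1+k)]. For k = 10% the bracket is 1.10 − 0.909 = 0.191, giving 0.134 at R = 0.70 and 0.162 at R = 0.85.

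**Step 2: share of variance due to dominance.** Share = 0.25·gap² / (0.25·gap² + 0.20²). For k = 10%, R = 0.70: 0.00446 / 0.04446 = 10%.

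**Step 3: shift at a 5-patient imbalance.** Shift = gap × 5/15.

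| k | Gap (points) | Variance share | Shift at 5/15 (points) |
|---|---|---|---|
| 0% | 0 | 0% | 0 |
| 5% | 7–8 | 3–4% | 2.3–2.8 |
| 10% | 13–16 | 10–14% | 4.5–5.4 |
| 15% | 20–24 | 19–26% | 6.5–7.9 |

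The standard error of the arm difference is SD × √(2/15): 7.3 points at SD 20 and 5.5 at SD 15. At k = 10% the shift is therefore 0.61–0.74 SE or 0.81–0.99 SE respectively.

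**Step 4: how often an imbalance arises.** With independent binomial counts, the SD of the imbalance is √(2 × 0.25/15) = 0.183, or 18 percentage points. A difference of 3 or more patients occurs in 36% of trials, 4 or more in 20%, and 5 or more in 9.9%. With p = 0.4 or 0.6 the last figure is 9.2%. If the total of dominant-side fractures is held fixed, it is 14.3% at exactly 15 of 30 but 6.6% at 14 or 16. The binomial value of about 10% is the fairer summary. If only 12 per arm reach the functional tests (illustrative), the SD of the imbalance rises to 20 percentage points.

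**Step 5: bias and error rate.** In 100,000 simulated trials with no cast effect (R = 0.70, SD 0.15, p = 0.5), the unadjusted arm difference averaged 0.0003, which is zero within simulation error. Its type I error was 0.049–0.050 at k = 5% and 10%. Adding the dominance indicator:
- kept type I error at 0.050;
- lowered the SD of the arm difference from 0.0602 to 0.0559 at k = 10%, a variance reduction of 1 − (0.0559/0.0602)² = 14%;
- lowered it from 0.0562 to 0.0559 at k = 5%, a reduction of 1%;
- at a 5-patient imbalance with k = 10%, cut the mean shift from 0.046 to 0.002 and the rejection rate from 9.8% to 5.3%.

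**Step 6: price of the indicator.** The adjusted SD of 0.0559 does not depend on k. With no dominance effect the unadjusted SD is 0.15 × √(2/15) = 0.0548, so estimating an unneeded term inflates variance by (0.0559/0.0548)² − 1, about 4%. The shares in Step 2 are before this cost.

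**The case against.** A reader might infer that chance imbalance in dominance biases the grip comparison. It does not: allocation is randomised, the unadjusted estimator is unbiased over randomisations, and its confidence interval already carries the extra variance. What stands is a loss of precision, and a shift conditional on an unlucky allocation.

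A reader might also infer that the plan has decided against adjustment. It is silent on covariates for the secondary models, which leaves the matter open. That is still a reason to settle it now, since choosing the term after seeing an imbalance is what prespecification avoids.

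Extending the argument to ROM is not supported. The mechanism is strength, and the documents give no dominance effect for ROM. They give none for grip either, so every magnitude here is conditional on the assumed k. At k = 5% the gain is roughly cancelled by the cost of the term.

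Finally, grip is peripheral. The secondary aim under Objectives names ARCEQ, comfort, EQ-5D-5L, cost-effectiveness and adverse events, and grip appears only in the list of outcomes. This is fair, and it sets the priority of the point. It does not remove the point, because the remedy uses data already in Table 2.

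**Conclusion.** The point holds as a minor improvement to one secondary outcome, grip strength. The planned analysis makes no stated use of affected wrist and dominance, although the uninjured hand is the only reference. If the dominant hand is 5–15% stronger, dominance accounts for about 3–26% of the variance in the grip ratio; if it is not stronger, for none. A 5-patient or larger imbalance occurs in about 10% of trials, and at a 10% effect a 5-patient imbalance moves the realised difference by about 4.5–5.4 points, up to about one standard error. These figures rest on 1:1 allocation, half of fractures on the dominant side, R = 0.70–0.85 and a residual SD of 20 points (15 for the upper standard-error figure). None of these is in the documents. Validity of the unadjusted test is not at issue.

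**What to change.** Add to Data analysis, Secondary outcomes: injured-side grip at the functional-test visits will be modelled with study arm, the same-visit uninjured-side grip, and an indicator for dominant hand injured, derived from affected wrist and hand dominance in Table 2. This also settles how the two sides are compared. Treat the same model for ROM as optional. State at the same time whether functional tests take place at T4 only or at T4 and T5, since the text and Table 1 differ.

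The cost is SAP wording and two model terms (the uninjured-side value and the indicator) in a sample of at most 30. If dominance has no effect, the indicator costs about 4% in variance. The uninjured-side value is measured after randomisation, so the model assumes that cast type does not change that hand; the plan's own side-to-side comparison already relies on this. No new data, visits or patients are needed.

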Both cost-effectiveness (CEA) and cost-utility (CUA) analysis will be performed from a societal perspective. For the calculation of medical costs, we will use charges as published in Singapore guidelines as a proxy of real costs. The unit per price of the cast application in patients with DRF will be calculated with the microcosting method. Intramural costs (i.a. additional diagnostics, number of hospital visits, in case of hospital admission the length of stay etc.) are collected from the electronic health record. Productivity costs will be registered in detail by the iPCQ. The iMCQ and the iPCQ are validated by the Institute of Medical Technology Assessment (Erasmus University, Rotterdam, The Netherlands).

The difference in costs and effects of CASTomize instead of a circumferential cast will be calculated as incremental cost-effectiveness ratio (ICER). The primary effect outcome measures will be the number of re-displacements for the CEA and quality-adjusted life years (QALY) for the CUA. QALYs will be measured, based on the Singaporean tariff for the EQ-5D-5L.

The sensitivity analysis will assess the robustness of the results to changes in costs and effect parameters. Bootstrapping with 1000 replications will be used to estimate 95% confidence intervals around cost differences and the uncertainty surrounding the ICERs. This will be graphically presented on cost-effectiveness planes and acceptability curves using the net benefit framework. For the time horizon of 6 months, discounting is not necessary.

Data management

All data are handled confidentially and anonymized in compliance with the Singapore Personal Data Protection Act (PDPA). Personal data of participants will be changed by a study number. This number is used for all study documentation, study reports and publications. The key of this study number will be handled by an independent researcher. During the study period, all data will be collected and managed using GemsTracker electronic data capture tools. Paper case report forms are entered in GemsTracker by the researcher and the original paper case forms will be filed in the investigator site file at the recruiting hospital. All data is stored for 10 years.

Data monitoring

Since the study is labelled as low risk, a data safety monitoring board is not required.

References

- [1] M. Neubauer, "DASH Score," *Heartbeat Medical*, Jul. 22, 2021. <https://heartbeat-med.com/resources/dash-score/> (accessed Nov. 06, 2022).

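### The closed list of serious adverse events has no general seriousness criterion, so some serious harms, and conversion to surgery for displacement, have no stated route to independent review during the trial

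*Combined protocol and SAP*

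**What the plan says.** - **Outcome, Secondary outcomes.** The last item reads "Number of conversions to surgical treatment and other (serious) adverse events will be monitored", with skin complications as the example. The next paragraph expects some patients to displace at week 1 or 2 and go on to fixation, after which trial procedures end. It does not say how such operations are reported.
- **Adverse events reporting, recording.** "All adverse events reported by the patient or observed by the treating physician or researcher will be recorded".
- **Adverse events reporting, onward reporting.** "Serious adverse events (SAE) will be reported to the Domain Specific Review Board (DSRB), which approved the protocol". No other class of event is said to leave the trial team.
- **Adverse events reporting, definition.** An SAE is one of three things: "Skin related problems requiring surgical intervention (Eg: Ulcer, infection, necrosis"), "Compartment syndrome", or a cast-related injury that costs a limb or life. A further list, of study-related SAEs, contains compartment syndrome alone.
- **Data monitoring.** "Since the study is labelled as low risk, a data safety monitoring board is not required".
- **Data analysis, Secondary outcomes.** Conversions and complications are compared by Fisher's exact or a chi-squared test.
- **Group 1.** "The Castomize 4D printed cast is appropriately heated and then moulded to the patients wrist".
- **Background.** On bench testing the new casts "were found to be less stiff and with a lower load to failure". The following sentence records the judgement that this did not matter clinically.

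**The concern.** An SAE definition normally rests on what happened to the patient, with named events as illustrations. Here the named events are the whole definition. An event can be serious by any ordinary standard (a hospital stay, lasting impairment) and still not qualify. The outcomes text adds uncertainty by listing conversion beside adverse events that may be serious, while the definition omits it. A coordinator cannot tell from the protocol whether an operation for displacement should be sent to the DSRB.

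In a trial without a safety board, SAE reporting is the only stated path by which anyone outside the team learns of harm while patients are still being enrolled. At stake is timely outside sight of serious harm with a new device, and a clear status for an outcome that the protocol itself expects.

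**Working it through.** The plan gives no figure to reproduce on this point. The check is to set each kind of event against the three-item definition and then against the stated routes.

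| Event | On the SAE list? | Recorded by the team? | Stated to go to the DSRB? |
|---|---|---|---|
| Skin ulcer, infection or necrosis needing an operation | Yes | Yes | Yes |
| Compartment syndrome | Yes | Yes | Yes |
| Cast injury costing a limb or life | Yes | Yes | Yes |
| Burn or skin injury treated in hospital without an operation | No | Yes | No |
| Lasting nerve injury without compartment syndrome | No | Yes | No |
| Operation for loss of reduction | No | Yes | No |

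1. The definition introduces its items as what SAEs are. It has no wording such as *including* and no general criterion, so it reads as closed. The examples in the skin item illustrate kinds of skin problem and do not relax the condition that surgery is needed.
2. Only SAEs are stated to be reported, so the last three rows stop at the trial team. The Data monitoring section supplies no second route, and no interim look by arm is described anywhere.
3. For conversions no rate is needed. None of those done for displacement is on the list, so the reportable number is zero at any rate.

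**Can the planned between-arm comparison stand in for reporting?** The Abstract gives 30 patients in total. The allocation ratio is not stated; I assume 15 per arm.

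- Two-sided Fisher test, 0 versus k events: p = 2 × C(15,k) / C(30,k).
  - k = 4: 2 × 1365 / 27405 = 0.100.
  - k = 5: 2 × 3003 / 142506 = 0.042.
- Chance of at least one event among 15 patients: 1 − (1 − p)^15, where p is the true rate. This is 14% at a rate of 1%, 54% at 5% and 79% at 10%.
- One-sided 95% upper limit after 0 of 15: 1 − 0.05^(1/15) = 18.1%.

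The comparison would flag only a large imbalance, no interim timing is given for it, and a clean arm would still be compatible with a rate of about 18%. In a trial of this size, serious harm has to be recognised case by case, which is the purpose of SAE reporting.

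**The case against.** The case on the other side has real force.

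- **The events are not hidden.** A reader might infer that the new cast's main harms reach no reviewer at all. The documents do not support that. All adverse events are recorded, conversions are monitored and compared between arms, and displacement, the step before conversion, is the primary outcome at 1, 2 and 6 weeks. Table 1 also schedules cast comfort at T1 to T3 and a photograph at T1. The gravest skin harms and compartment syndrome do go to the DSRB. Nor can one infer that the final results would omit these events, since conversions and complications have their own planned analysis.
- **The two paragraphs are not in flat contradiction.** With *serious* in parentheses, the natural reading is adverse events of either kind. The sentence makes conversion an adverse event, not necessarily an SAE.
- **Exempting an expected outcome event is common practice.** This stands as a principle, but the protocol never states the exemption. The paragraph on expected failures deals with surgery and the end of trial procedures, not with reporting.
- **Heat injury is an inference.** It follows from the heating step alone; no temperature, burn risk or prior event is given. The bench result must likewise be read with the judgement that it was clinically unimportant, although the protocol gives no evidence for that judgement.
- **The trial is small and labelled low risk.** That supports doing without a safety board. It does not support a narrow SAE definition, because that definition then governs the only stated outside route.

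What survives is the absence of a seriousness criterion, the unstated status of conversion, and the missing independent route for both.

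**Conclusion.** The point holds in this limited form and should be corrected. As written, the rule leaves some serious cast-related harms and every conversion for displacement outside SAE reporting. No other route to independent review during the trial is stated for them. The trial team does see and record these events.

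The conclusion rests on reading the three-item list as exhaustive, which is how it is worded, and on these documents alone; any DSRB reporting rules held elsewhere could narrow the gap and cannot be checked here. It does not depend on a conversion rate, on heat injury being likely, or on the new cast being worse. The figures on the planned comparison assume 15 per arm and serve only as context. Whether the list of study-related SAEs is too short is a separate question.

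**What to change.** 1. Reconcile the last item of the secondary outcomes with the adverse events reporting section, so that conversion has the same status in both.
2. Define an SAE by its outcome, identically in both arms: death, threat to life, hospital admission or its prolongation, lasting impairment, or an intervention needed to prevent one of these. Keep the three listed events as examples.
3. State whether conversion to surgery is reported to the DSRB as an SAE or is an exempt outcome event. The statement must be explicit: under an outcome-based definition, any conversion involving admission becomes an SAE unless exempted.
4. If conversion is exempt, state that conversion counts are included in the routine reports to the DSRB. The protocol does not describe such reports, so it should name them.

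The cost is protocol wording, a matching change to the adverse event form, a somewhat larger reported SAE count and a few more DSRB reports. No safety board, extra visit or change to treatment is needed.
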